### changed to

"The study drugs can cause irritation of the stomach or intestine. Most people with this problem have only mild symptoms. Rarely, the irritation can cause an ulcer or perforation (hole) in the stomach or intestine. In older people who are **not** taking medicines like the study drugs, serious problems like a bleeding ulcer or hole in the stomach or intestine occur at a yearly rate of 0.5%, (that is, in about 5 people out of every 1000.) Sometimes people have to be hospitalized for these problems. Most of these people recover fully, but a small number die. In the study's first 17 months, bleeding ulcers or perforation occurred in ADAPT participants at a yearly rate of 0.6%. Since bleeding from the stomach or intestine can cause a low blood count, we will check your blood count at least twice a year while you are in ADAPT. If you develop stomach or intestine problems, you will stop taking the study drug."

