### changed to

- "Use of ≥4 doses per week of either of the following in the 14 days prior to the enrollment visit:
  - non-aspirin NSAIDS or aspirin (>81 mg per day)
  - histamine H2 receptor antagonists"
- "History of hypersensitivity or anaphylactoid response to sulfa drugs or other NSAIDs (such as aspirin, ibuprofen, celecoxib, naproxen)"

changed to

"History of hypersensitivity or anaphylactoid response to sulfonamide antibiotics (e.g., Bactrim, Septra, Gantrisin, Gantanol, Urobak), or to aspirin or other NSAIDs (e.g., ibuprofen, diclofenac, celecoxib, naproxen)"

The following change was made to section 4.3:

"Serious adverse events must be reported to the Coordinating Center within 1 working day of the field site personnel learning of the event."

changed to:

"Serious adverse events thought to be possibly, probably, or definitely associated with use of study drug must be reported to the Coordinating Center within 1 working day of the field site personnel learning of the event."

The following changes have been made to the prototype consent statements in Appendix C:

- The five prototype consent statements have been revised to reflect the transfer of the Chairman's Office from the Johns Hopkins University to the University of Washington.
- The Risks/Discomforts section of the prototype ADAPT Participant Consent Statement for Enrollment has been revised as follows:

"The study drugs can cause stomach irritation. This can range from mild stomach upset to ulcers. Very rarely, people with ulcers bleed from their stomachs. In older people who are **not** taking medicines like the study drugs, a bleeding ulcer occurs in about 5 people out of every 1000 in 1 year. Sometimes people have to be hospitalized for a bleeding ulcer. Most people recover, but a small number die from a bleeding ulcer. We do not think taking celecoxib will increase your risk of a bleeding ulcer much, if at all. Taking naproxen may increase your risk to about 10 in 1000. We will monitor you for any problems of this sort. If you develop any stomach problems, you will stop taking the study drug."

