### **Exclusion criteria**

- History of peptic ulcer disease complicated by perforation, hemorrhage or obstruction
- History of uncomplicated peptic ulcer with symptoms in the 28 days prior to the enrollment visit
- Clinically significant hypertension, anemia, liver disease or kidney disease according to guidelines provided in the ADAPT Handbook
- History of hypersensitivity or anaphylactoid response to sulfonamide antibiotics (e.g., Bactrim, Septra, Gantrisin, Gantanol, Urobak), or to aspirin or other NSAIDs (e.g., ibuprofen, diclofenac, celecoxib, naproxen)
- Concurrent use of warfarin, ticlopidine or any other type of anti-coagulant
- Concurrent use of systemic corticosteroids

- Use of ≥ 4 doses per week of either of the following in the 14 days prior to the enrollment visit:
  - non-aspirin NSAIDs or aspirin (> 81 mg per day)
  - histamine H2 receptor antagonists
- Current plasma creatinine ≥ 1.5 mg/dL
- Enrollment in any trial that is likely to interfere with ADAPT procedures or affect treatment outcomes
- Cognitive impairment or dementia according to criteria specified in the ADAPT Neuropsychology Manual
- Current alcohol abuse or dependence
- Any condition that, in the opinion of the study physician, makes it medically inappropriate or risky for the participant to enroll in the trial

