#### 12. Protection of human subjects

#### 12.3. Risks and potential benefits to participants

**Risks**: There are risks to participation in ADAPT for each treatment group. Like all participants, those assigned to placebo will be asked to limit the use of NSAIDs and other medications (see section 3.3). Thus, participants in this group may have an increased burden of pain or inflammation, for example.

Participants assigned to receive naproxen sodium or celecoxib may experience adverse effects of the study drug, such as water retention, increased blood pressure, stomach irritation, gastrointestinal bleeding, anemia, renal toxicity, or hepatotoxicity. The risk of serious adverse events is expected to be higher in the naproxen sodium group than in the celecoxib group.

The above risks are outlined in the Participant Consent Statement for Enrollment (see Appendix C). Participants are told that they may withdraw from the study at any time and that they may stop the study drug in order to take proscribed medications. Safety monitoring is described in section 12.4.

**Potential benefits**: If one or both of the active study treatments are found to be efficacious, participants taking the efficacious treatment(s) may benefit from delayed onset or prevention of AD. It also is possible that participants receiving naproxen could benefit from a lower risk of heart attack, stroke, and certain cancers, although these effects are still under investigation.

All participants may benefit from the regular, ongoing, medical monitoring and referrals (when indicated) that they will receive in ADAPT. Those who develop dementia while in the trial may benefit from early diagnosis, which could facilitate appropriate treatment and care. In addition, all participants may benefit from the satisfaction of contributing to medical knowledge.

Alternatives to participation: Because ADAPT is a primary prevention trial, there is no direct alternative to participation. Other primary prevention trials are in progress, but the geographical location of the participating sites for the most part does not coincide with that of the ADAPT sites. Because the study medications are available either over the counter (naproxen sodium) or by prescription (celecoxib), people interested in the prevention of AD could self-medicate. However, given the unknown safety and efficacy of such use, it is not an advisable alternative to study participation.

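### The 0.6% yearly bleeding rate in the Version 1.4 enrollment consent reads as an average over all three arms, placebo included, so it is not the risk of taking either study drug and should be labelled as an average

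*Protocol*

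**What the plan says.** The Protocol's Document history, under Version 1.4 (the latest version), gives the replaced and the current text of one paragraph in the Risks/Discomforts section of the enrollment consent.

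- **Replaced text.** For older people not on such medicines, "a bleeding ulcer occurs in about 5 people out of every 1000 in 1 year". For naproxen, "Taking naproxen may increase your risk to about 10 in 1000". Celecoxib was expected to add little or nothing.
- **Current text.** For older people not on such medicines, bleeding ulcer or a hole in the stomach or intestine is said to "occur at a yearly rate of 0.5%, (that is, in about 5 people out of every 1000". It then reports that, over the first 17 months, "bleeding ulcers or perforation occurred in ADAPT participants at a yearly rate of 0.6" (per cent). It says that the study drugs can cause ulcer or perforation and that a small number of those affected die. It gives no separate statement for either drug.

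Sections 3.1 and 3.4 set masked allocation at 1:1:1.5 for naproxen, celecoxib and placebo. Section 12.3 lists gastrointestinal bleeding among the drug risks and states: "The risk of serious adverse events is expected to be higher in the naproxen sodium group than in the celecoxib group". It adds: "The above risks are outlined in the Participant Consent Statement for Enrollment".

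**The concern.** The paragraph offers two numbers, a rate without such drugs and a rate in the trial. A reader will naturally take the gap of 0.1 percentage point a year as what the study drugs add. But the trial rate names no arm, so on its plain reading it includes the placebo group, the largest of the three. An average that is 3/7 placebo dilutes any excess in a single active arm.

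What is at stake is how clearly a serious and occasionally fatal harm is conveyed to people deciding whether to enroll, 2 in 7 of whom will be assigned naproxen. Section 12.3 also relies on the consent to convey these risks and still ranks naproxen above celecoxib for serious adverse events. The bleeding paragraph no longer does so.

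**Working it through.** **Can the 0.6% be reproduced?** No. The Protocol gives neither an event count nor person-years for the first 17 months. What can be checked is what an all-arm rate of 0.6% says about naproxen.

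**Inputs**
- Shares from 1:1:1.5 (section 3.4): naproxen 1/3.5 = 2/7, celecoxib 2/7, placebo 1.5/3.5 = 3/7. Using these as shares of person-time assumes similar follow-up by arm, which is reasonable with permuted blocks of 7 or 14.
- Background 0.5% a year (both consent texts).
- Naproxen 1.0% a year and celecoxib about background (replaced text).
- Stopping of active drug: 15% in the first year (section 3.2).

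**Forward check.** Pooled rate = (2 × naproxen + 2 × celecoxib + 3 × placebo)/7.
- Replaced text's figures: (2 × 1.0 + 2 × 0.5 + 3 × 0.5)/7 = 4.5/7 = 0.643%, printed 0.6%.
- With 15% of the naproxen group off drug throughout, its rate is 0.5 + 0.85 × 0.5 = 0.925%. Pooled: (1.85 + 1.0 + 1.5)/7 = 0.621%, still 0.6%.
- Celecoxib at 0.525%, full adherence: (2.0 + 1.05 + 1.5)/7 = 0.650%, the rounding boundary.
- Celecoxib at 0.55%: (2.0 + 1.1 + 1.5)/7 = 0.657%, printed 0.7%. So the match needs celecoxib close to background.

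**Inverse check.** With celecoxib and placebo both at 0.5%, naproxen = (7 × pooled − 5 × 0.5)/2.

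| Pooled rate | Implied naproxen rate | Ratio to 0.5% |
|---|---|---|
| 0.55% | 0.675% | 1.35 |
| 0.60% | 0.85% | 1.7 |
| 0.65% | 1.025% | 2.05 |

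Every row is consistent with a printed 0.6%. If instead both active drugs carried the same rate, it would be (7 × 0.60 − 3 × 0.5)/4 = 0.675% at a pooled 0.60%.

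**Precision.** Person-years must be assumed. At 1,000 person-years, 0.6% is 6 events, with an exact Poisson 95% interval of 0.22% to 1.31%. At 2,000 it is 12 events, 0.31% to 1.05%. Sampling error therefore widens the range well beyond rounding.

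**Endpoint.** The replaced background and naproxen figures were for bleeding ulcer. The current figures cover bleeding ulcer or perforation, with the background unchanged at 0.5%. The two sets are therefore not strictly the same outcome, and the forward check is approximate.

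**The case against.** The strongest reply is that the 0.6% is stated truthfully, as a rate in trial participants, and that it suits someone who does not yet know the assignment: it is the average risk of enrolling. On the replaced text's own figures, the average excess from enrolling is (2/7) × 0.5 = 0.14 percentage point, close to the 0.1 point the paragraph suggests. This stands. It justifies keeping the figure but not leaving it unlabelled, because the sentence sits in a description of what the study drugs can do and follows a rate without such drugs.

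A second reply is that masking rules out arm-level rates. It does for observed rates, but the replaced text gave an expected naproxen figure under the same masking, so a statement from outside data unmasks nobody.

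A third is that only this one paragraph can be read. Appendix C is not available, and the Version 1.3 history shows that drug-specific wording on celecoxib was also added to this consent. Naproxen's bleeding risk may be singled out elsewhere. This stands too, and makes part of the fix conditional.

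A reader might also infer a flat contradiction with section 12.3. The documents do not go that far. Section 12.3 gives no rate and speaks of serious adverse events generally, and the current paragraph nowhere says the two drugs are equal.

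**Conclusion.** The point holds as one of labelling and disclosure. On its plain reading, the 0.6% is an average in which 3 in 7 participants take no active drug, so it is not the risk of either study drug. It is compatible with a naproxen rate of about 1.0% and equally with about 0.68%, and so neither confirms nor excludes a doubling. This rests on four assumptions: unqualified participants means all arms; person-time follows the allocation ratio; celecoxib and placebo are near 0.5% (celecoxib below about 0.525% at full adherence for the 1.0% case); and adding perforation to the outcome changes little.

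Two stronger readings are not supported. A reader might infer that naproxen doubles the risk and that the consent conceals this. The arithmetic shows compatibility only, the 10 per 1000 stands only in superseded text, and the reason for removing it is not given. A reader might also argue that excluding people with a "History of peptic ulcer disease complicated by perforation, hemorrhage or obstruction" makes the trial's true background lower than 0.5%, and naproxen's excess larger. No background rate for screened participants is given, the reference group is described only as older people, and entry at age 70 or above could act in the other direction.

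No estimand, analysis or sample size is affected. The change is worth making because it is cheap and concerns a serious harm.

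**What to change.** 1. In the consent paragraph, label the 0.6% as the masked average over all three treatment groups, about 3 in 7 of whom take no active drug.
2. Check the rest of the enrollment consent. If it carries no naproxen-specific bleeding statement, add one beside the 0.5% background, based on the sponsor's current external estimate and referring to the same outcome (bleeding ulcer or perforation).
3. Reconcile the paragraph with section 12.3, so that the expected ordering of naproxen and celecoxib stated there is either outlined in the consent or revised in both places.

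The cost is consent wording and IRB resubmission. No unmasking, new data or change to the analysis is needed.

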### **ADAPT Protocol**

### **Source documents**

The following document is partially excerpted and partially adapted from the following source documents:

- The grant application for this project
- Other protocols developed at the Johns Hopkins Center for Clinical Trials

### **Executive summary**

An intervention that delays onset of Alzheimer's disease (AD) by several years would yield huge public health benefits. Several studies suggest that non-steroidal anti-inflammatory drugs (NSAIDs) may produce such a delay. NSAIDs may also attenuate progressive age-related cognitive decline (ARCD) when this condition represents a prodrome of AD. Both outcomes can be evaluated definitively only in randomized trials. Such trials can also examine attendant risks of long-term NSAID use in the moderate doses that appear to afford protection against AD and ARCD. Improved safety may be available with selective cyclooxygenase-2 (COX-2) inhibitors, but, owing to the newness of these compounds and the lack of relevant data, it is not known whether COX-2 inhibition offers the protective effect apparent with conventional NSAIDs.

The Alzheimer's Disease Anti-inflammatory Prevention Trial is a randomized, placebo-controlled, multicenter trial designed to test the efficacy of a non-selective NSAID and a selective COX-2 inhibitor for the prevention of AD and attenuation of ARCD. The treatment regimens, which are tested in parallel, are: naproxen sodium (220 mg b.i.d.), celecoxib (200 mg b.i.d.), and placebo. The trial is designed to enroll 2,625 dementia-free participants who are age 70 or older and have a history of Alzheimer-like dementia in a first degree relative. Participants will be evaluated with structured, standardized methods of assessment and diagnosis. Conspicuous decline in periodic cognitive assessment test results will identify participants with suspected incident dementia, who will then undergo further assessment.

The proposed sample size presumes 7 years of followup, with estimates of incidence beginning at 2.5% for the first year and increasing by a factor of 1.1 per year. It also takes into account attrition through mortality and other causes, and treatment "drop-outs" and "drop-ins." It should provide 80% power (2-tailed  $\alpha$ =0.05) to detect a 30% reduction in either active treatment group.

### 1.1. Public health significance of Alzheimer's disease and age-related cognitive decline

Dementia and cognitive decline are common, well-recognized public health problems of old age. Numerous studies now suggest that the prevalence of dementia after age 85 exceeds 30%. Alzheimer's disease (AD) is by far the most common age-related dementia. It has recently been projected that the prevalence of AD will nearly quadruple to 8.94 million cases in the U.S. in 50 years. Current annual U.S. expenditures on this dreaded illness are believed to exceed \$90 billion. The prevention of AD is thus a top public health priority.

The elderly are also prone to milder cognitive syndromes that have been grouped under such rubrics as "benign senescent forgetfulness" and "age-associated memory impairment." In some instances these conditions portend more serious cognitive disorders, notably AD. Although called "mild," these disorders are a major hindrance to the daily functioning of millions. Their reported occurrence varies widely with criteria for their identification, but their frequency increases with age. Given the well known growth in the elderly population of the developed world, particularly the marked growth in the numbers of those aged 85 and older, these milder cognitive disorders may become comparable to dementia as a source of disability and a target for prevention.

### 1.2. Potential for prevention of Alzheimer's disease

Evidence is growing for the perspective that AD pathogenesis evolves chronically, with latent and prodromal phases. Fundamental to this perspective is the discovery of the importance of the APOE genetic locus that encodes the lipid transport protein apolipoprotein E. For some time it has been known that genotype at APOE modifies risk of AD. It is now clear that APOE also influences cognitive ability, neural anatomy, and central nervous system metabolism in a preclinical or latent period that precedes AD dementia by many years. Thus, in cognitively normal elderly male dizygotic twin pairs who were discordant for the high-risk  $\varepsilon 4$  allele at APOE, the men with  $\varepsilon 4$  scored lower than their twin brothers on some cognitive tests. Similarly, in a population-based study of individuals over age 70, non-demented subjects with \$4 showed greater cognitive decline over 4 years than did individuals without ε4. Work by Ohm^8 suggested that Alzheimer-like neurofibrillary changes may begin 50 years before onset of dementia symptoms, and that this process is again influenced by genotype at APOE. MRI volumetric studies, including investigations of monozygous twin pairs, showed reduced hippocampal volumes in association with the £4 allele. Finally, £4 was associated with reduced parietal glucose metabolism (suggestive of decreased neural activity) in normal relatives of AD cases with mild memory complaints. Altogether, these findings support the notion that there are genotype-related latent processes in the brains of individuals who develop AD, and that these changes appear decades before onset of dementia. The existence of a prolonged latent phase in the AD process may make it possible to intervene in this phase and delay or prevent its progression to age-related cognitive decline (ARCD) and dementia.

### 1.3. Potential for attenuation of age-related cognitive decline

For decades there has been debate over whether, and under what circumstances, mild cognitive impairment may progress to AD. The foregoing notion of AD as an extended process with a long latent phase and a shorter prodrome suggests that longitudinal cognitive change may denote an incipient Alzheimer process. Thus, there is growing adherence to the notion that progressive (even if mild) cognitive decline may represent an end of a continuous and unimodal distribution of age-related change, with AD at its opposite extreme. Accordingly, severity of deficit or more restrictive criteria (viz., those suggesting progression or other stigmata of early Alzheimer change) have been used to identify persons who are more likely to "convert" to clear-cut dementia within a short time of observation. Thus, Katzman found that severity of deficit at baseline was a strong predictor of subsequent decline. Flicker found that 72% of 32 subjects with "mild cognitive impairment" had declined significantly after 2 years. Rubin followed clinic patients with "very mild senile dementia of the Alzheimer type" and found similar rates. O'Connor studied a representative community sample and found that 12 out of 24 subjects with "minimal dementia" progressed to at least "mild dementia" after 2 years. In a large longitudinal study of the Cambridge (UK) population, one-third of subjects who meet criteria for mild dementia progress within 2 years to show moderate to severe dementia.

Several population studies have suggested that cognitive decline (in addition to dementia incidence) is related to the presence of APOE  $\epsilon 4$  alleles. Henderson's study of 638 subjects found trends associating  $\epsilon 4$  dose with decline. Feskens et al. showed a similar relationship (p = 0.02) among a somewhat older Dutch cohort. Hyman et al. studied the Iowa EPESE cohort (1899 subjects) over 4 to 7 years. They found a significant but weak association (p = 0.045) between  $\epsilon 4$  (and also  $\epsilon 2$ , which may be protective) and decline on a delayed recall task. The association of APOE and ARCD adds substantially to the argument that the latter may be a prodrome of AD.

### 1.4. Overview of prospects for the prevention of Alzheimer's disease

The foregoing findings suggest that AD and some instances of ARCD have common antecedents and, possibly, common mechanisms. They may thus be susceptible to common means of prevention. Several strategies are available for such efforts at prevention:

- **Identification and investigation of genetic markers:** The discovery of such markers for AD, and the ongoing search for new genes, have spurred efforts to uncover their mechanisms of action. The discovery of these mechanisms could then lead to rational treatment and/or prevention strategies, but such strategies are not yet available for testing.
- Identification of risk factors for intervention strategies: Early epidemiologic research into environmental modification of AD risk focused principally on the identification of factors associated with increased occurrence of the disease. However, the factors discovered, such as increased age, imputed genes, and head injury, are not readily amenable to prevention strategies.

• Interventions based on identification of environmental factors associated with decreased occurrence of AD: A surprising result of the search for environmental modifiers of AD risk was the finding that several common exposures appeared to be associated with decreased occurrence of AD. These exposures include non-steroidal anti-inflammatory drugs (NSAIDs), hormone replacement therapy (in post-menopausal women), anti-oxidants (possibly including red wine), and histamine H2 receptor antagonist drugs. A number of the above have been tested as treatments in patients with AD, and most have not proven effective. However, by the time AD is definitively diagnosed, its pathogenic processes may no longer be amenable to intervention. Therefore, despite its failure as a treatment, a given compound could still delay the latent stage mechanisms of AD, and thus prevent the emergence of dementia symptoms or ARCD. Because considerable observational evidence suggests that prevention may be possible using NSAIDs, this trial will test the prevention efficacy of two different NSAIDs.

